5.3. Software

- All analyses will be performed using **Microsoft Excel (Version 16.83)**. No specialized statistical software was used due to the simplicity and exploratory nature of the data.

6. Data Handling and Quality Assurance

- Clinical data were extracted from patient medical records and entered manually into a study-specific Excel spreadsheet.
- Double-checking was conducted for critical variables (e.g., blood loss, time intervals) by both study investigators.

7. Limitations

- Small sample size prevents generalizability.
- No control group.
- Estimates of blood loss may be subject to observer bias.

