Study Protocol

Title

Temporary Aortic Occlusion with the Abdominal Tourniquet for Refractory Postpartum Haemorrhage: A Proof-of-Concept Study in a War-Affected Region

Version

1.0

Date

November 1, 2024

Principal Investigators

[name], MD, PhD — Olexandrivska Hospital, Zaporizhzhia

[name], MD, PhD, DMSc — Uniklinika Medical Centre, Kyiv

Institution

Olexandrivska Hospital, Zaporizhzhia, Ukraine

Ethics Approval

Approved by Olexandrivska Hospital Ethics Committee (Approval number: 2024/EC/128094)

1. Background and Rationale

Postpartum haemorrhage (PPH) remains the leading cause of maternal mortality globally, especially in low-resource and crisis-affected settings. In Ukraine, full-scale war has disrupted medical infrastructure, limiting access to timely surgical interventions and blood transfusion.

The AAJT-S (Abdominal Aortic and Junctional Tourniquet – Stabilized) is an FDA-approved device for temporary aortic occlusion in trauma, but its use in obstetrics is not well studied. This study aims to evaluate the feasibility, safety, and preliminary clinical efficacy of AAJT-S in controlling refractory PPH due to uterine atony in a wartime environment.

2. Objectives

Primary Objective:

- To assess whether the AAJT-S device can temporarily and safely control severe PPH in a resource-limited, high-risk setting.

Secondary Objectives:

- To describe feasibility of AAJT-S deployment by obstetric teams.
- To evaluate maternal hemodynamic stabilization and procedural outcomes.

- To monitor for short- and long-term complications (thrombosis, ischemia, infection, renal dysfunction).

3. Study Design

- Design: Prospective, open-label, non-randomized, proof-of-concept
- Duration: December 2024 – April 2025
- Setting: Olexandrivska Hospital, Zaporizhzhia, Ukraine
- Sample Size: 4 patients

4. Inclusion/Exclusion Criteria

Inclusion Criteria:

- Age \geq 18 years
- Primary PPH with blood loss >1000 mL
- Refractory to uterotronics and uterine balloon tamponade
- Oral informed consent obtained

Exclusion Criteria:

- PPH due to trauma, coagulopathy, or retained placenta
- Inability to provide informed consent

5. Intervention

Application of the AAJT-S device over the upper abdomen (inflated to 250 mmHg) to achieve temporary aortic occlusion for \leq 60 minutes. Device application was done following persistent bleeding despite standard therapy.

6. Procedures

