1.2. Secondary Objectives

- To evaluate the safety profile of the AAJT-S device (device-related complications, thrombotic events, ischemic injuries, infection).
- To assess the duration of bleeding control and time to definitive surgical intervention.

2. Study Design

- **Design:** Prospective, single-center, open-label, non-randomized, proof-of-concept study.
- **Sample Size:** 4 patients
- **Analysis Type:** Descriptive statistics only. No inferential testing or hypothesis-driven comparisons will be performed due to small sample size and exploratory nature.

3. Analysis Populations

- **Full Analysis Set (FAS):** All patients who received AAJT-S for refractory PPH.
- **Safety Population:** Identical to FAS; all patients who underwent device placement and were monitored until discharge.

4. Variables

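### Past-tense text in the SAP and protocol conflicts with the prospective label, so the SAP outcomes that differ from Protocol 7 are not shown to have been fixed before the four women's data were seen

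*SAP*

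**What the plan says.** Protocol 3 gives the design as "Design: Prospective, open-label, non-randomized, proof-of-concept", and SAP 2 says "Prospective, single-center, open-label, non-randomized, proof-of-concept study". The protocol is version 1.0, dated "November 1, 2024", and Protocol 3 gives the study period as "Duration: December 2024 – April 2025".

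Several sentences nevertheless describe completed work:

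- Protocol 5: "Device application was done following persistent bleeding despite standard therapy".
- SAP 5.3: "No specialized statistical software was used due to the simplicity and exploratory nature of the data".
- SAP 6: "Clinical data were extracted from patient medical records and entered manually into a study-specific Excel spreadsheet".
- SAP 6: "Double-checking was conducted for critical variables (e.g., blood loss, time intervals) by both study investigators".

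The SAP puts the analysis itself in the future tense in sections 2, 5.2 and 5.3. In 5.3 this happens in the same bullet as the past-tense software sentence. The text available for review shows no SAP date and does not say what had been seen when the SAP was finalised.

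**The concern.** This is an open-label study of four women with no control group, tests or intervals. No error rate is at stake. The main protection against selective or reshaped reporting is an outcome list fixed before anyone knows the results.

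SAP 6 reads like an account of finished work: it names the source, the spreadsheet, the kinds of variable checked and who checked them. If that section was written with the data in hand, the outcome list in SAP 4 may have been written then too. That would matter little if SAP 4 repeated the protocol's list, but it does not. A report that called every SAP variable pre-specified would claim a protection that the documents do not demonstrate.

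**Working it through.** No figure in the plan needs reproducing. The check compares dates, tenses and outcome lists.

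**Dates.** From 1 November 2024 to the earliest possible start, 1 December 2024, is 30 days. At face value the protocol precedes all device use in the study, so the sentence in Protocol 5 describes as done something that had not yet happened.

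**Tense.** Past wording in the population definitions (SAP 3) is normal and is not counted.

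- Completed action: one statement in Protocol 5 and four verbs in the SAP (software used, data extracted, data entered, double-checking conducted).
- Future action: five verbs in the SAP (one in section 2, three in 5.2, one in 5.3).

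The division is roughly between data handling, described as past, and analysis, described as future. That pattern would fit a SAP written after data collection and before analysis. It would also fit loose drafting.

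**Effectiveness variables, SAP 4.2 against the protocol.**

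| SAP 4.2 variable | Protocol 7 | Elsewhere in the protocol |
|---|---|---|
| Time to bleeding control | Changed form of the primary outcome | – |
| Duration of placement | Not listed | Foreseen: Protocol 5 limits occlusion time |
| Definitive surgery | Not listed | Foreseen: Protocol 6 describes surgical treatment |
| Blood loss | Listed | – |
| Transfusion | Listed | – |

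The count is 2 listed + 1 changed + 2 not listed = 5.

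**The changed outcome.** Protocol 7 asks a yes/no question: was bleeding controlled within 2 minutes of application? SAP 4.2 records minutes from inflation until visible bleeding stops, sets no threshold and labels nothing primary. The yes/no result can be recovered from the minutes only if application and inflation are the same moment, which neither document states. If inflation comes later, the SAP clock gives the shorter time. With four women, one reclassified case moves the proportion controlled by 1/4 = 25 percentage points.

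**Safety variables, SAP 4.3.** Of the five, thrombosis, ischaemia and infection are named in Protocol 2. Device-related complications and readmissions are covered only in general terms, by the adverse events in Protocol 6 and the postoperative complications and long-term recovery in Protocol 7.

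**In the protocol but without a SAP variable.** Readiness time gained (Protocol 7) has none in SAP 4.2, although SAP 1.2 has time to definitive surgery among its objectives. Renal dysfunction (Protocol 2) has none in SAP 4.3.

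**The case against.** The strongest reply is that tense does not date a document, and that the argument cuts both ways. If past tense shows late writing, the sentence in Protocol 5 casts doubt on Protocol 7 as well. If the protocol's date is trusted, these authors sometimes use the past tense for future events, and the same habit in the SAP proves little. A SAP date before December 2024, possibly in the removed text, would reduce the conflict to a drafting error. All of this stands, and it is why Protocol 5 must be reconciled together with the SAP.

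A second reply is that there is little room for favourable choices. Protocol 8 already fixes medians, ranges and case-by-case presentation, and SAP 5.1 repeats the median and range. Placement duration and surgery were foreseeable data items. This stands for the choice of summary. It does not answer the lost 2-minute threshold or the two protocol items with no SAP variable, because individual listings show only what was recorded and reported.

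A reader might also infer that the study is really retrospective because data came from medical records. The documents do not support that: taking data from records is compatible with prospective enrolment and treatment.

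**Conclusion.** The conflict between the prospective label and the past-tense text is real, and pre-specification of the SAP outcomes is not demonstrated. The exposure is limited to specific items: one changed primary outcome, two effectiveness variables outside Protocol 7, two safety variables covered only in general terms, and two protocol items with no SAP variable. Blood loss, transfusion, thrombosis, ischaemia and infection are not affected, because the protocol names them.

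A reader might go further and conclude that none of the SAP outcomes can be called pre-specified, or that three of the five effectiveness variables were chosen after the results were known. The documents support neither. The first ignores the outcomes that the protocol names. The second treats a difference between two lists as evidence of timing and motive.

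The conclusion takes the date on Protocol v1.0 at face value, an assumption that Protocol 5's own wording weakens. It also rests on the visible text alone, so the lack of a visible SAP date is not counted against the plan.

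**What to change.** 1. Reconcile the tenses in Protocol 5 and SAP 5.3 and 6, and state how many women's outcomes had been seen when the SAP was finalised.
2. Report the Protocol 7 outcomes first, with control within 2 minutes of application as the primary outcome and readiness time gained among the secondary outcomes.
3. Add a column to the results table marking each variable that is absent from, or changed since, Protocol v1.0 as post hoc, unless earlier specification is documented. Treat blood loss, transfusion, thrombosis, ischaemia and infection as named in the protocol.
4. Account for renal dysfunction: report it, or say that it was not assessed.
5. Do not relabel the design merely because data came from medical records.

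The cost is a few sentences and one table column. The downside is a slightly less favourable description of some outcomes.
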